2.1. Objectives The objective of the study is to determine long-term trends of a 5-day FMD meal program in patients already subjected to FMD in a previous trial (NCT05698654) and that will continue an FMD-based plan to assess its long-term effect on fat mass maintenance. The secondary objectives are to determine long-term trends of a 5-day FMD meal program in patients already subjected to FMD who will continue an FMD-based plan to assess its long-term effect on the maintenance of body weight, body mass index, blood pressure, IGF-1, haemoglobin A1c, fasting glucose, LDL, total cholesterol, C-Reactive Protein, and the proportion of participants who received medications at baseline.

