2.2. Endpoints

- 2.2.1. *Primary endpoint*: maintenance of at least 50% of the fat mass lost during the previous trial and measured after one follow up year on FMD every 3 months
- 2.2.2. *Secondary endpoints*: maintenance of at least 50% of one or more risk factors improvements achieved during the previous clinical trial and measured after one year of follow up FMD cycles every 3 months including improvements in: body mass, body mass index, blood pressure, IGF-1, haemoglobin A1c, fasting glucose, LDL, total cholesterol, and C-Reactive Protein. Determine long-term trends in the reduction/stabilization in the use of antihypertensive and glucose-lowering drugs or other commonly used medications.

3. Study Design

Follow up clinical trial including participants of the approved studies “*Studio degli effetti della dieta mima-digiuno e della dieta della longevità sulla composizione corporea, fattori di rischio per malattie età-correlate e marcatori dell'invecchiamento in uno studio randomizzato*” and “*Studio degli effetti della dieta mima-digiuno e della dieta della longevità sulla composizione corporea, fattori di rischio per malattie età-correlate e marcatori dell'invecchiamento in uno studio randomizzato-2*” that will follow 5-day of the FMD meal program every three months, for one year.

Selection and withdrawal of subjects of the previous clinical study

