3.1.2. Exclusion Criteria

- individuals who are allergic to tree nuts (macadamia, cashew, almond, pecan), soy, oats, sesame, or celery/celeriac;
- pregnant females;
- any documented cancer diagnosis within the past 5 years;
- documented myocardial infarction within past 5 years;
- documented cerebrovascular accident within past 5 years;
- chronic steroid use (longer than 45 consecutive days);
- insulin-dependent diabetes mellitus;

- individuals taking insulin or insulin-like drugs and individuals taking hypoglycemic agents other than metformin. In this last case, close attention will therefore be paid to the self-monitoring of blood glucose during the FMD cycles;
- Individuals with severe hypertension (systolic greater than 200 mmHg and or diastolic greater than 105 mmHg).

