3.1.3. Prohibited Medications, Medical Foods or Nutritional Supplements

- Change in prescription medications, over-the-counter (OTC) medications, medical foods, and nutritional supplements within 30 days prior to the start and for the duration of the study.
- Use of medications classified as narcotics 15 days prior start and for the duration of the study.
 - Use of prescription medications and/or over-the-counter medications for acute and semi-acute medical conditions 15 days prior to start and for the duration of the study. Use of acetaminophen is permitted on an as-needed basis.
 - Use of an investigational drug or participation in an investigational study within 30 days prior to the start and for the duration of the study.
 - Use of anticoagulant medications (heparin compounds or warfarin) within 30 days prior to the start and for the duration of the study. Use of aspirin 400 mg once daily is permitted
 - Subjects will not be allowed to discontinue prohibited prescription medications to meet enrolment criteria.

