During the first follow-up visit, the study staff will assess the signs and symptoms of adverse events and review compliance to the FMD program. The visit will also include body composition assessment using BIA, measurement of height, weight, and vital signs, medical history and current medications. Participants will receive the FMD boxes for the remaining two cycles together with the ketone test strips for self-monitoring of urinary ketone bodies during the FMD cycles.

Follow-up visit 2

During the second follow-up visit, the study staff will assess the signs and symptoms of adverse events and review compliance to the FMD program. This visit will also include body composition assessment using BIA, measurement of height, weight, and vital signs, medical history and current medications. In addition, a collection of fasting blood for haematological and for the genetic analyses will be performed.

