4.2. Prohibited Medications and Procedures

No concomitant prescription medications, over-the-counter medications, medical foods, and nutritional supplements are to be started, or doses changed during the study unless they are prescribed by the subject's primary care giver for treatment of a specific clinical event.

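### Stable drug use is listed as a secondary endpoint, yet the medication rules largely require it, so unchanged use cannot be read as a benefit of the FMD

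*Protocol*

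**What the plan says.** **Endpoint.** Section 2.2.2 asks for long-term trends in the "reduction/stabilization in the use of antihypertensive and glucose-lowering drugs or other commonly used medications". Section 2.1 lists, among the things whose maintenance under the FMD is to be assessed, "the proportion of participants who received medications at baseline".

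**Rule in 3.1.3.** The prohibited list includes "Change in prescription medications, over-the-counter (OTC) medications, medical foods, and nutritional supplements within 30 days prior to the start and for the duration", meaning until participation ends. A separate bullet prohibits "medications for acute and semi-acute medical conditions 15 days prior to start and for the duration of the study", with as-needed acetaminophen permitted (4.3 repeats this).

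**Rule in 4.2.** "No concomitant prescription medications, over-the-counter medications, medical foods, and nutritional supplements are to be started, or doses changed during the study", followed by the exception "unless they are prescribed by the subject's primary care giver for treatment of a specific clinical event". The rule names starts and dose changes. It does not name stops.

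**Entry restriction in 3.1.2.** Excluded are "individuals taking insulin or insulin-like drugs and individuals taking hypoglycemic agents other than metformin".

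**Comparator.** All participants receive the FMD. Section 8.6 plans within-arm change from baseline and a comparison with the control arm of the previous study.

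**Data collection.** Table 1 marks medications at screening, T0 and T2. The text for follow-up visit 1 adds "measurement of height, weight, and vital signs, medical history and current medications" at T1. Section 8.4 mentions medication logs.

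**The concern.** An endpoint should be free to move with the treatment. Here the protocol tells participants to keep their medication constant and then lists constancy as one of the two favourable results. A year of unchanged prescriptions could be reported as an effect of the diet when it mainly shows that participants followed the rules. The more informative result is a cut in antihypertensive or metformin dose because it is no longer needed. Section 3.1.3 prohibits that change, and it is not clearly within the 4.2 exception.

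The protocol also gives two answers to the same question. If a participant's doctor prescribes a new drug or a dose change for a clinical event, 4.2 accepts it and 3.1.3 prohibits it. Read literally, 3.1.3 even prohibits a dose cut that the participant medically needs.

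**Working it through.** No arithmetic applies: the protocol states no number of medication users, no expected rate of change and no threshold for this endpoint. The maximum of 267 subjects in 8.1 is not split by medication use. The check is to set the rules side by side for each kind of change during the year.

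| Change during the study | 3.1.3 | 4.2 | Reading under 2.2.2 |
|---|---|---|---|
| None | Required | Default without a clinical event | Stabilization |
| Start or increase for a clinical event | Prohibited | Allowed if primary care prescribes it | Increase |
| Dose cut for a clinical event, such as symptomatic hypotension | Prohibited | Plausibly allowed | Reduction |
| Dose cut because blood pressure or glucose improved | Prohibited | Not clearly within the exception | Reduction |
| Stop | Prohibited as a change | Not named | Reduction |
| Drug for an acute condition, other than acetaminophen | Prohibited | Allowed if primary care prescribes it for an event | Not specified |

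Three things follow.

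1. **The default is stabilization under either rule.** Without a clinical event, 3.1.3 leaves no permitted outcome other than unchanged use. Section 4.2 leaves only stops, on which it is silent.

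2. **The two rules disagree** on changes made for a clinical event and on acute-condition drugs other than acetaminophen.

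3. **The glucose-lowering part has little room to move.** Given 3.1.2, metformin is the only glucose-lowering drug that a participant can bring into the study. A reduction from the T0 regimen is therefore a cut or stop of metformin, which 3.1.3 prohibits.

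The comparison planned in 8.6 does not separate the rules from the diet. The previous trial's control arm was not followed alongside these participants over the same 12 months. Section 1.2 describes the intervention programmes of that trial as lasting 6 months.

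**The case against.** The best defence has four parts.

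**Section 3.1.3 is eligibility text.** It stands among the selection criteria, and its last bullet concerns meeting enrolment criteria. On this reading 4.2 alone governs conduct, and 4.2 does not bar stops and allows changes for clinical events. This is a fair reading, but 3.1.3 says in terms that it runs for the length of the study, which an entry check cannot test. Even under 4.2 alone, unchanged use remains the default, so the point about interpretation stands.

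**Drug use is not frozen.** A reader might infer that medication cannot change at all and that the endpoint carries no information. The documents do not support that. Primary care can prescribe under 4.2, a medication change is not itself listed among the individual stopping rules in 7.4.5, and medications are recorded at each visit. Nor is it right that any fall in glucose-lowering use over the year must concern metformin brought in at entry: a drug started under the 4.2 exception could later be reduced. The endpoint is constrained, not fixed.

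**Much of the problem is the missing concurrent control.** This is true. Attribution would be weak under any medication rule, and 2.2.2 asks only for trends and sets no success threshold. But 2.1 speaks of the long-term effect of the FMD, and the rules add a second explanation for stable use that no comparison in the plan removes.

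**Constant background medication protects other endpoints.** This also stands. Blood pressure, glucose, HbA1c, LDL and total cholesterol are easier to interpret when treatment is stable. It is a reason not to insist that reductions be permitted merely because readings improved.

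A reader might also infer that different sites would handle the same prescription differently. The protocol refers to a single study site, so the conflict is one of instruction, not of variation between sites.

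**Conclusion.** The concern holds in limited form. Unchanged medication is largely what 3.1.3 and 4.2 require. Without a concurrent control it cannot be read as a benefit of the FMD. Separately, 3.1.3 and 4.2 contradict each other on changes made for clinical events and on drugs for acute conditions other than acetaminophen.

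The size cannot be stated in numbers. One secondary item is affected, and the fat mass endpoint is untouched. The priority is low: a change worth considering, because it is cheap and alters what may be concluded from this item.

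The conclusion assumes that the trend is measured over the follow-up year, from T0 to T2. If it were measured from the previous trial's baseline, changes made before the 30-day window could count, but the protocol does not say so and those changes would precede the follow-up FMD cycles.

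**What to change.** 1. **Align the rules.** Keep in 3.1.3 the pre-entry stability window and the bans on narcotics, anticoagulants and investigational drugs. Replace its on-study bar on medication changes and on acute-condition drugs with the 4.2 rule and its clinical-event exception. State that medically needed dose cuts or stops, for example for hypotension or hypoglycaemia, fall within the exception.
2. **Reword the endpoint.** In 2.2.2, remove stabilization as a benefit. Report reduced, unchanged and increased use from T0 to T2 separately and descriptively, and word 2.1 to match.
3. **Flag affected participants.** Mark those with a relevant medication change in the blood pressure, glucose, HbA1c and lipid analyses.

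Whether to permit reductions merely because readings have improved is for the sponsor to decide. It would make the endpoint more informative at the expense of constant background treatment.

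**Cost.** A protocol amendment, which under 9.2 needs ethics committee approval. Medications are already collected, but the protocol does not say that the dose and the reason for a change are recorded, so those fields may have to be added. Compared with a strict reading of 3.1.3, background medication becomes slightly less constant. The flag shows that confounding but does not remove it.

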3.1.1. Inclusion Criteria

Individuals already included in the aforementioned previous studies *who were assigned to one of the 2 intervention arms: Fasting mimicking diet or fasting mimicking diet plus Longevity diet* and who completed the study less than 6 months prior to starting the new study. Blood tests and a nutritional assessment will be conducted, serving as the baseline for the new study.

3.1.2. Exclusion Criteria

- individuals who are allergic to tree nuts (macadamia, cashew, almond, pecan), soy, oats, sesame, or celery/celeriac;
- pregnant females;
- any documented cancer diagnosis within the past 5 years;
- documented myocardial infarction within past 5 years;
- documented cerebrovascular accident within past 5 years;
- chronic steroid use (longer than 45 consecutive days);
- insulin-dependent diabetes mellitus;

- individuals taking insulin or insulin-like drugs and individuals taking hypoglycemic agents other than metformin. In this last case, close attention will therefore be paid to the self-monitoring of blood glucose during the FMD cycles;
- Individuals with severe hypertension (systolic greater than 200 mmHg and or diastolic greater than 105 mmHg).

3.1.3. Prohibited Medications, Medical Foods or Nutritional Supplements

- Change in prescription medications, over-the-counter (OTC) medications, medical foods, and nutritional supplements within 30 days prior to the start and for the duration of the study.
- Use of medications classified as narcotics 15 days prior start and for the duration of the study.
 - Use of prescription medications and/or over-the-counter medications for acute and semi-acute medical conditions 15 days prior to start and for the duration of the study. Use of acetaminophen is permitted on an as-needed basis.
 - Use of an investigational drug or participation in an investigational study within 30 days prior to the start and for the duration of the study.
 - Use of anticoagulant medications (heparin compounds or warfarin) within 30 days prior to the start and for the duration of the study. Use of aspirin 400 mg once daily is permitted
 - Subjects will not be allowed to discontinue prohibited prescription medications to meet enrolment criteria.

3.1.4. Medical History and Concurrent Diseases

- A history of allergy or intolerance to study products. Detailed descriptions of study product are included in Section 4.1 and 4.2, appended to the Study Informed Consent.
- Clinically significant vital sign abnormalities (systolic blood pressure <90 mmHg or >200 mmHg, diastolic blood pressure <50 mmHg or >105 mmHg or resting heart rate of <50 or >100 bpm) at screening visit.
- A serious, unstable illness including cardiac, hepatic, renal, gastrointestinal, respiratory, endocrinologic, neurologic, immunologic, or hematologic disease.
- Known infection with HIV, TB or Hepatitis B or C.
- A current diagnosis or personal history of:
 - any cardiovascular disease including myocardial infarction, angina, cardiovascular surgery (within 5 years), congestive heart failure, cardiac arrhythmias or conduction abnormalities, cerebrovascular accident, transient ischemic attack (TIA), or peripheral vascular disease, deep vein thrombosis or pulmonary embolus. Diabetes mellitus requiring inhaled or injected insulin.
 - Any significant liver or kidney disease such as cirrhosis or non-alcoholic fatty liver disease, glomerulonephritis, and/or ongoing dialysis treatment.
 - Any malignancy (with the exception of adequately treated malignancies with no known recurrence for >2 years).
- Any serious mental illness including a history of attempted suicide.

- Any medical condition that in the opinion of the primary care doctor or a specialist would preclude safe participation in this study or interfere with compliance.

3.1.5. *Substance Use*

- History of regular intake of >14 alcoholic drinks per week for females, and >21 drinks per week for males (1 drink = 35 cl. beer, 12 cl. wine, or 30 ml. hard liquor).

3.1.6. *Technical reasons*

Any condition in which bioelectrical impedance testing would be impossible or uninterpretable (e.g. prostheses in extremities on both sides, limb amputation, implanted pacemaker, inability to lay still or supine, or skin defects on preferred electrode placement sites).

3.1.7. *Other Exclusion Criteria*

Inability to comply with study and/or follow-up visits.

- Any concurrent condition (including clinically significant abnormalities in medical history, physical examination or laboratory evaluations) which, in the opinion of the PI, would preclude safe participation in this study or interfere with compliance.
- Any sound medical, psychiatric and/or social reason which, in the opinion of the PI, would preclude safe participation in this study or interfere with compliance.
- Abnormal laboratory findings including: abnormal blood counts (haematocrit < 33% or > 47%; WBC < 3.0 or > 12.0 $\times 10^3/\text{mm}^3$; platelets < 140 or > 500 $\times 10^9/\text{L}$); abnormal kidney function test (creatinine > 2.5 mg/dL) or liver function test(s) (AST, ALT, alkaline phosphatase) > 1.5X the upper limit of normal; serum calcium > 11 mg/dL; serum K < 3.5 mEq/L; Na < 134 or > 148 mmolL⁻¹

3.1.8. *Women of Childbearing Potential*

Contraception: the effects of the study products on the developing human fetus have not been studied extensively. For this reason, women of childbearing potential must agree to use adequate contraception (hormonal or barrier method of birth control; abstinence) prior to study entry and for the duration of study participation. Females of childbearing potential will have a pregnancy test prior to receiving study products. Should a woman become pregnant or suspect she is pregnant while participating in this study, she should inform study staff and her primary care physician immediately.

Pregnancy: because there is an unknown but potential risk for adverse events in pregnant women during treatment with the study products, pregnant women are not eligible for study participation.

Breast-feeding: Because there is an unknown but potential risk for adverse events in nursing infants secondary to treatment of the mother with the study products, breastfeeding mothers are not eligible for study participation.

3.2. *Recruitment*

The participants will be identified within the intervention groups of the previous clinical studies (*Studio degli effetti della dieta mima-digiuno e della dieta della longevità sulla composizione corporea, fattori di rischio per malattie età-correlate e marcatori dell'invecchiamento in uno studio randomizzato 1 and 2*) who are willing to start a new study for other 12 months, and who completed the study less than 6 months prior to starting the new study and achieved the study's objectives. Blood tests and a nutritional assessment will be conducted, serving as the baseline for the new study. The recruitment period will last up to 3 years

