3.3. Scheduled clinical visits

The assessment schedule (Table 1) lists all the assessments and when they are to be performed. Subjects will meet with study staff. When the visit doesn't include blood collection or BIA the visit can be made remotely. During the clinical visits, staff will review calendars, assess for signs and symptoms of adverse events, review compliance to the study product and answer any questions from the subject. Eligible participants will receive 3 different visits (Baseline visit (t0), and two follow-up visits (after 6 and 12 months from the baseline). Eligible participants will be telephonically contacted at the end of each FMD cycle (day 6) in order to assess signs and symptoms of adverse events, compliance to the nutritional intervention (see Appendix A, B), to answer to the questionnaire for dietary recall (see Appendix C).

4. Table 1 reports the timeline of the clinical visits and the activities scheduled. All data obtained from these assessments must be supported in the participant's source documentation.

	Screening Visit	Baseline visit (T ₀)	Follow-up visit 1 (T ₁)	Follow-up visit 2(T ₂)
Informed Consent	✓			
Review Eligibility Criteria	✓			
Start of intervention				
Physical examination ¹		✓	✓	✓
Vital Signs ²	✓	✓	✓	✓
BIA		✓	✓	✓
Peripheral Blood for genetic analysis		✓		✓
Hematological analyses ³		✓		✓
Pregnancy test	✓	✓		✓
AE and SAE collection		✓	✓	✓
Primary and secondary endpoints assessment		✓	✓	✓
Medications	✓	✓		✓

¹ height, weight (dress weight), waist and hip circumferences. ² Body temperature, blood pressure, pulse, respiratory rate. ³ Lipid profile (total cholesterol, LDL-cholesterol, HDL-cholesterol and triglycerides, serum/plasma, albumin, alkaline phosphatase, insulin-like growth factor 1 (IGF-1), Insulin-like growth factor-binding protein 1 (IGFBP1), creatinine, insulin, C-reactive protein (CRP),

aspartate aminotransferase (AST), alanine aminotransferase (ALT), homocysteine, glucose, glycosylated hemoglobin (HbA1c).

Screening and Baseline visit

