Potential participants already subjected to a 5-day fasting-mimicking diet (FMD) program either alone or in combination with the longevity diet previously enrolled in one of the two interventional arms and who completed the clinical study NCT05698654 less than three months before the enrolment period will be contacted *via* telephone to determine preliminary eligibility and interest. Once participants meet all inclusion/exclusion criteria, they will be offered by study staff the opportunity to learn more about the research opportunity before any procedure is performed. Participants meeting eligibility will be then invited to attend a baseline and two follow-up visits

Baseline visit will include measurement of height, weight, and vital signs (body temperature, blood pressure, pulse, respiratory rate), completion of medical history questionnaire, review of medical history and current medications, and collection of fasting blood (12 mL: 6 mL for serum, 6 mL for plasma). Blood testing will include: complete blood count (CBC), glycated hemoglobin (HbA1c), glucose, insulin, lipid profile (total cholesterol, LDL-cholesterol, HDL-cholesterol and triglycerides), AST (GOT), ALT (GTP), alkaline phosphatase, creatinine, reactive C protein (PCR), albumin, insulin, IGF-1, IGFBP1, homocysteine as well as a urine pregnancy test in females of child-bearing potential. Fasting is defined as 12 hours of refraining from consumption of food and beverages though unlimited consumption of water is allowed and encouraged. Participants will be given three boxes of FMD together with ketone test strips to self-monitor urinary ketone bodies during the FMD cycles. Detailed information on the FMD plans will be also given during the visit. Baseline visit will also include body composition assessment using Bioelectrical Impedance Analysis (BIA), measurement of height, weight, and vital signs, medical history, current medications and a collection of fasting blood for the genetic analysis (25 mL: 7.5 mL for serum, 7.5 mL for plasma, 10 mL for white blood cells). Note, the typical draw volume for blood donation in Italy is ~450 mL. Blood testing information will be also retried from the screening visit.

Follow-up visits

The follow-up visits will be carried out after three (follow-up visit 1) and five (follow-up visit 2) FMD cycles (6 and 12 months), in order to evaluate the progress of the trial.

Follow-up visit 1

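### No pregnancy test is scheduled at follow-up visit 1, where the last two FMD boxes are handed out; the only on-study test comes after the final cycle

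*Protocol*

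**What the plan says.** Section 3.1.8 (Women of Childbearing Potential) excludes pregnant women because "there is an unknown but potential risk for adverse events in pregnant women during treatment with the study products". It requires contraception before entry and throughout participation, and it states that "Females of childbearing potential will have a pregnancy test prior to receiving study products".

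Section 3.3 presents Table 1 as the complete list of assessments and their timing. Its row "Pregnancy test" is ticked at screening, T0 and T2, and is blank at T1. The text for the screening and baseline visit agrees with the table at that point: the blood tests are listed "as well as a urine pregnancy test in females of child-bearing potential".

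On timing, section 3 (Study Design) describes participants "that will follow 5-day of the FMD meal program every three months, for one year". The text under Follow-up visits places them "after three (follow-up visit 1) and five (follow-up visit 2) FMD cycles (6 and 12 months"). Three boxes are given at baseline. At follow-up visit 1, "Participants will receive the FMD boxes for the remaining two cycles together with the ketone test strips".

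**The concern.** Study product is handed out at two visits, T0 and T1, and only the first has a pregnancy test. The one test scheduled after product use begins is at T2, when all five cycles are over. It can lead to follow-up of a pregnancy that was exposed, but it cannot stop the exposure.

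The protocol's own reason for excluding pregnancy applies to cycles 4 and 5 as much as to cycle 1. T1 is the only staff visit between T0 and the end of product use, and section 5.1.5 does not ask participants to return boxes. T1 is therefore the last in-person point at which an unrecognised pregnancy could be found before two more boxes leave the site. At stake is avoidable exposure in a group that the protocol means to keep unexposed. Nothing statistical depends on it.

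**Working it through.** No figure in the protocol needs reproducing. The check sets the test schedule beside the dispensing schedule and then counts months since the last test.

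**Inputs**
- Pregnancy tests: screening, T0 and T2; none at T1 (section 3.3, Table 1).
- Boxes: three at T0 (baseline visit text) and those for the remaining two cycles at T1 (follow-up visit 1 text). 3 + 2 = 5 cycles, which agrees with T2 coming after five.
- Visits: T1 after cycle 3, at 6 months; T2 after cycle 5, at 12 months (Follow-up visits).
- Cycle interval: three months, for one year (section 3).

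**Schedules side by side**

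| Visit | Month | Cycles completed | Boxes given | Pregnancy test |
|---|---|---|---|---|
| T0 | 0 | 0 | 3 | yes |
| T1 | 6 | 3 | 2 | no |
| T2 | 12 | 5 | 0 | yes |

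Dispensing visits with a test: 1 of 2. Tests after T0 and before the last cycle: 0.

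**Months since the last test, by cycle**

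Assumption: cycles at months 0, 3, 6, 9 and 12. This spacing fits both the three-month interval and the visit timing. Gap = month of the cycle minus month of the most recent test; the T1 test is taken at month 6, after cycle 3.

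| Cycle | Month | Gap now (last test at month 0) | Gap with a T1 test |
|---|---|---|---|
| 1 | 0 | 0 | 0 |
| 2 | 3 | 3 | 3 |
| 3 | 6 | 6 | 6 |
| 4 | 9 | 9 | 9 − 6 = 3 |
| 5 | 12 | 12 | 12 − 6 = 6 |

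- Now: mean (0 + 3 + 6 + 9 + 12)/5 = 30/5 = 6.0 months; longest 12 months.
- With a T1 test: mean (0 + 3 + 6 + 3 + 6)/5 = 18/5 = 3.6 months; longest 6 months.
- Cycles 4 and 5 alone: mean (9 + 12)/2 = 10.5 months now, and (3 + 6)/2 = 4.5 months with the test.

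**Without the spacing assumption**

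Cycles 4 and 5 lie between T1 (month 6) and T2 (month 12) however they are spaced. Each therefore runs 6 to 12 months after the last test as the schedule stands, and a T1 test shortens both intervals by 6 months.

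**Feasibility**

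Section 3.3 allows a remote visit only when it does not "include blood collection or BIA the visit can be made remotely". T1 includes BIA in both Table 1 and the visit text, so it is held in person and a urine test can be done there.

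**The case against.** The strongest objection is that nothing here is contradicted. Section 3.1.8 does not say whether the test must precede each dispensing or only the first. On the second reading, screening and T0 comply in full, and what remains is an opinion about how often to retest. That stands as far as it goes: this is not a breach. The placement of the on-study test is still poor, because it comes when it can no longer protect anyone.

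Other safeguards exist. Contraception is required throughout, a known or suspected pregnancy must be reported at once (3.1.8 and 7.3.6), staff call after every cycle, medical history is taken at T1, and product can be held or stopped (7.4.3 and 7.4.5). They reduce the risk, but none of them detects a pregnancy that the woman has not recognised, and each call comes after that cycle's food has been eaten.

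The blank cell could also be unreliable. The Medications row is blank at T1 too, although the visit text includes current medications there. Nor does silence in the T1 text prove much, since the T2 text also omits the pregnancy test that Table 1 ticks. This lowers certainty about what was intended. Even so, neither table nor text provides a T1 test, and if one was intended the same correction is needed.

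Finally, months since a test measure the schedule and not the probability of exposure. The product is food taken for five days every three months, section 9.2 calls the study minimal risk, and the number of women of childbearing potential is not given. All of this is fair, and it limits the point to a minor one.

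**Conclusion.** The point holds as a minor, inexpensive safety improvement. One of the two dispensing visits has no pregnancy test, and the only on-study test follows the last cycle. Cycles 4 and 5 run 6 to 12 months after the last test; this rests only on the stated timing of T1 and T2. The falls in the longest interval and in the mean rest on the assumed cycle months of 0, 3, 6, 9 and 12.

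The gain is partial. A T1 test finds a pregnancy present on that day, not one that begins later, and cycles 2 and 3 would still rely on the T0 test. The size of the risk cannot be estimated from the protocol.

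**What to change.** Add a urine pregnancy test at T1 for women of childbearing potential, done before the boxes for cycles 4 and 5 are handed out. Tick it in Table 1 and name it in the follow-up visit 1 text. Keep the T2 test, so that pregnancies exposed during cycles 4 and 5 are still found and followed; the T1 test is an addition and not a move.

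The cost is one urine strip per woman of childbearing potential, at a visit already held on site, plus one tick and one line of text. Section 8.1 foresees at most 267 participants of both sexes, so fewer than 267 strips would be needed if any participant is male or past childbearing age. A home urine test before each cycle would also cover cycles 2, 3 and 5, but that is a larger change and is not needed for this correction.
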